##### *Sample Size Estimation*

In a one-way ANOVA study, sample sizes of 522, and 522 are obtained from the 2 groups whose means are to be compared. The total sample of 1044 subjects achieves 90% power to detect differences among the means versus the alternative of equal means using an F test with a 0.05 significance level. The size of the variation in the means is represented by the effect size  $\eta^2 = \sigma_m^2 / (\sigma_m^2 + \sigma^2)$ , which is 0.01 [10-13]

##### *Dropout-Inflated Sample Size*

Average Group Sample Size n	Group	Dropout Rate	Sample Size Ni	Dropout-Inflated Enrollment Sample Size Ni'	Expected Number of Dropouts Di
522	1-2	10%	522	580	58
	Total		1044	1160	116

Average Group Sample Size n	Group	Dropout Rate	Sample Size Ni	Dropout-Inflated Enrollment Sample Size Ni'	Expected Number of Dropouts Di
522,00	1 - 2	10%	522	580	58
	Total		1044	1160	116

#### 6.5. PROCEDURES

Participants entering the study after meeting exclusion/exclusion criteria (Table 1), give written informed consent (informed consent and patient information sheet, see Appendix 1) and they are assigned to a cohort (Figure 1). Cohorts are divided into:

- 1) Healthy pre-cohort: HCW exposed to but not infected with SARS-CoV-2, negative PCR-test or Ig M (N) and IgG (N)
- 2) Non-recent Infected cohort: HCW infected with SARS-CoV-2 (>15 days RT-PCR, positive)
- 3) Recent Infected cohort infected HCW : HCW with acute SARS-CoV-2 infection (<15 days RT-PCR, positive)

All participants undergo a standardised follow-up according to the specific cohort to which they are assigned (Table 2). At study entry, we record the following information: baseline socio-demographic

data, clinical data (symptoms), epidemiological data (contact with a positive and symptoms of COVID-19) (table 3), information on the work environment, data on the diagnosis of COVID-19 (previous biological samples taken and dates of sick leave due to COVID-19), use of personal protective equipment, previous health status and habits. At subsequent visits, epidemiological data, clinical data (symptoms) and vaccinations are recorded.

Finally, initial participant's cohort assignation is reviewed and reclassified on basis on laboratory results (RT-PCR test or SARS-CoV-2 antibodies IgM and IgG against the nucleocapsid (N)) in two final cohorts:

1) Health Care Workers Healthy Cohort (HCW\_H): This cohort includes HCW with negative laboratory test RT-PCR and SARS-CoV-2 antibodies IgM(N), and IgG(N).

2) Health Care Workers Infected Cohort (HCW\_I): This cohort includes HCW with positive laboratory test (RT-PCR and/or SARS-CoV-2 antibodies IgM and IgG) This cohort is subdivided into three categories according to the illness severity:

Asymptomatic or Presymptomatic Infection: Individuals with positive laboratory evidence of COVID-19 but no COVID-19 signs nor symptoms.

Mild-Moderate Illness: Individuals with positive laboratory evidence of COVID-19 who have any of the various signs and symptoms of COVID-19 (e.g., fever, cough, sore throat, malaise, headache, muscle pain, nausea, vomiting, diarrhea, loss of taste and smell) but who do not have shortness of breath, dyspnea, or abnormal chest imaging and home health care.

Severe-Critical Illness: Individuals with positive laboratory evidence of COVID-19 who have any of the various signs and symptoms of COVID-19 (e.g., fever, cough, sore throat, malaise, headache, muscle pain, nausea, vomiting, diarrhea, loss of taste and smell) and that have shortness of breath, dyspnea or abnormal chest imaging, treated in the hospital with or without admission to the ICU.

This whole process is being conducted by trained multidisciplinary research staff (family physicians, nurses, assistant manager and project manager). See Figure 1

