To date, seroprevalence studies conducted in Spain have used cross-sectional designs. Thus, they cannot provide systematic data on long-term antibody and cellular immune responses.

Thus, thorough serological and prospective studies are needed to determine whether ADE manifests among SARS-CoV-2 infections, either because of prior homologous infection or cross-reactive antibodies from other HCoVs. This will have particular relevance for vaccination plans.

Another interesting point that deserves further analysis is analyzing the different antibody specificities generated and their dynamics. Several studies have examined various types of antibodies identified against SARS-CoV-2 (Spike1, Spike2, Nucleocapsid, envelopes), identifying variable responses [8,9]. However, little is known about the simultaneous kinetics of the different antibodies over time. This can be analyzed with our cohort and also with the antigens used in the various vaccines that will be in the market in the next months. Thus, given the virus's short evolution, it is necessary to create an exhaustively monitored cohort. This cohort will make it possible to identify the kinetics of SARS-CoV-2-specific antibodies in individuals with different degrees of severity of COVID-19 and to know which levels of antibodies are protective against new possible reinfections in 3 years.

Crucially, this serological information will be used to strategically deploy HCW immune to the infection, limiting the risk of exposure and inadvertent propagation of the virus.

In conclusion, the present study is crucial to obtain epidemiological and clinical data to improve health policies for the prevention of SARS-CoV-2 infection. In addition, the study will be conducted simultaneously with the course of the pandemic, which will make it possible to obtain real-time data on the different waves that occur and, in turn, to study the SARS-CoV-2 endemic. Therefore, ProHEPIC-19 can be used as an ongoing platform to implement SARS-CoV-2 research projects with particular emphasis on incidence rate, reinfection, vaccines, and long term immune response.

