### 6.3. STUDY PERIOD

From March, 31 2020 until recruitment is finished (estimated on June, 15 2021).

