## 6.7. DATA SOURCES

We will simultaneously use various information sources

A) Database created for the register of ProHEPiC-19.

The data will be centralized in an internal centralized data warehouse from the Catalan Health Institute. After data collection and curation, the data is ready to be analyzed to (1) validate the accuracy on demographic, clinical, social, and psychological data of professionals; (2) register SARS-CoV-2 antibodies; (3) results in RT-PCR test.

B) Primary care electronic health records (e-Cap) contain demographic data and clinical variables: health conditions (ICD-10 codes) and diagnostic date, medication prescribed, comorbidities, lab test results (including RT-PCR).

C) Case Report Form (Teleform) specific for the study, which will include a specific identifier for the patient and the serological and immunological tests' information. This information will be shared among the various sources of information about the study employing individual, anonymized participants' identification. Immunological data will be collected to understand the vaccine's protection and the relationship between immune response and reinfection.

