## 12. DATA STORAGE AND SECURITY

### 1) Type and format of data collected/generated within the Project

All data will be processed in a pseudo-anonymised way by coding the identifying variables in both the initial paper data collection booklet (CB) and the subsequently created database. Only the necessary data to achieve the research objectives will be collected. The necessary variables to conduct the project are: 1) 1) Biological sex; 2)Age (years); 3) Academic level; 4) Housing characteristics ; 5)Occupational situation ; 6) Clinical Spectrum of COVID-19; 7) Clinical monitoring of COVID-19 Symptoms; 8) Date first symptoms; 9) Diagnostics. In the electronic medical records; 10) Use of personal protective equipment; 11) Medication prescribed; 12) Hospital admissions; 13) Comorbidities; 14) Mortality by all causes; 15) Psychosocial and healthy habits changes during pandemic; 16) Laboratory Assays: RT-PCR test, antibodies to SARS-CoV-2 ( IgM and Ig G against nucleocapside, IgG Against Spike) , INFg Elispot assays; Citokines multiplex assay; Combinatorial flow cytometry of lineage, inducible activation markers and intracellular cytokines. These variables can be consulted in the corresponding section of the methodology.

In accordance with Law 14/2007, the samples of each participant in the project will be collected directly from the person concerned and the procedure set out in the regulations on the use of biological samples will be followed to authorise their use. The samples will only be used for the project and will subsequently be destroyed.

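### The plan does not ensure that workers vaccinated before their first sample are identified, so spike antibody and spike T-cell results in positive workers may mix vaccine and infection response.

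*Combined protocol and SAP*

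**What the plan says.** **Data collection.** Section 6.5 sets out the entry data: socio-demographic, symptom and epidemiological data, work environment, COVID-19 diagnosis, and "use of personal protective equipment, previous health status and habits". Vaccination is not named. The following sentence places it later: "At subsequent visits, epidemiological data, clinical data (symptoms) and vaccinations are recorded".

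**Variable lists.** Neither the 16 covariables in 6.6 nor the matching 16 items in section 12 include vaccination. Section 12 introduces its list with "Only the necessary data to achieve the research objectives will be collected" and "The necessary variables to conduct the project are".

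**Who can enter, and when.** The criteria in 6.2.1 and Table 1 do not mention vaccination. Section 6.3 runs recruitment from 31 March 2020 to an estimated 15 June 2021, and the Abstract foresees a larger cohort until 2024. The Background expects "the antigens used in the various vaccines that will be in the market in the next months". Section 6.7 adds: "Immunological data will be collected to understand the vaccine's protection and the relationship between immune response and reinfection".

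**What is measured and analysed.** Spike IgG (outcome 6) is measured from baseline in workers positive by RT-PCR or serology (6.6, item 16 B). The ELISpot peptide pools behind outcome 7 include the S1 and S2 regions (item 16 C2). The kinetics models in 6.8.2.1 take all data from workers who ever tested positive and compare clinical spectrum and sex. Section 6.8.2.2 compares immune response across clinical spectrum and antibody levels between sexes. No analysis in 6.8 uses vaccination.

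**The concern.** The authors foresaw vaccination, but scheduled its recording only after entry. A worker who was infected and also vaccinated before the first blood sample would contribute a baseline spike value with two sources, and the plan would treat it as the response to infection. The same applies to T-cell responses to the spike pools.

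Two planned results are exposed. The kinetics curve for spike IgG would start from, and later follow, a mixture of responses. The comparison by clinical spectrum would be confounded if the vaccinated share differs between severity groups, for example if workers infected after vaccination tended to have milder illness (an assumption). A later decision to exclude or adjust for vaccinated workers needs the doses received before entry, whether recorded then or recovered afterwards.

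**Working it through.** **1. The plan's own figure, for a yardstick.** Section 6.4 gives 522 per group for 90% power at the 0.05 level with η² = 0.01.
- f = √(0.01/0.99) = 0.1005. For two equal groups, d = 2f = 0.201 SD.
- An exact noncentral F search gives n = 522 per group (power 0.9005), and 522/0.90 = 580 after dropout. Both figures reproduce.
- That calculation is for two groups in general. Spike IgG is not measured in the healthy cohort, so 0.201 SD serves here only as the size of difference the plan regards as worth detecting.

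**2. Can a worker enter after vaccination?** Eligibility does not prevent it. The recruitment window is 365 days (31 March 2020 to 31 March 2021) plus 30 + 31 + 15 = 76 days, or 441 days. The documents give no start date for staff vaccination, so the window is assumed. With uniform entry (also assumed):

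| Vaccination under way for the last | Share of entrants | Of 1350 | Of 675 infected |
|---|---|---|---|
| 90 days | 90/441 = 20.4% | about 275 | about 138 |
| 180 days | 180/441 = 40.8% | about 551 | about 276 |

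These count people who enter while vaccination is possible, not people vaccinated. If half of them had been vaccinated, the vaccinated share would be 10.2% or 20.4% of entrants. The share could also be near zero. The Abstract describes the 1350 as already making up the study, and the Background speaks of vaccines as still to come. If those two statements date from the same time, few or none of the 1350 were vaccinated at entry.

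**3. Effect on a group mean.** If a share p of a group is vaccinated before sampling and vaccination raises the marker by D SD (assumed, additive), the mean moves by p × D.

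| p | D = 1 | D = 2 |
|---|---|---|
| 10% | 0.10 SD | 0.20 SD |
| 20% | 0.20 SD | 0.40 SD |
| 40% | 0.40 SD | 0.80 SD |

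A shift of 0.201 SD is reached at p = 0.201/1 = 20% or p = 0.201/2 = 10%. In a comparison of two severity groups, the bias is (p₁ − p₂) × D. It is therefore zero if both have the same vaccinated share, and 0.20 SD if the shares differ by 20 points with D = 1.

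**4. Who is exposed.** Spike testing follows a positive RT-PCR or nucleocapsid result. It therefore covers infected workers and nucleocapsid false positives. At the stated specificity of 93.3%, 675 uninfected workers would yield 675 × 0.067 = 45 false positives on one test, or 675 × (1 − 0.933²) = 87 if IgM and IgG errors are independent and either result counts. A vaccinated false positive would contribute a spike value with no infection behind it.

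**The case against.** The strongest case against is that this is a matter of wording.

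- **Earlier doses can be recovered.** A reader might infer that workers vaccinated before entry cannot be identified. Section 6.5 does not limit the later record to doses since the last visit, previous health status at entry might cover vaccination, and the primary-care record is a named source. For non-recent infected workers, Table 2 as it can be read shows first bloods only at visit 4, when vaccination may be recorded anyway. This stands as a limit on the claim. But no section requires retrospective capture, or dose dates and product. Section 6.7 does not name vaccination among the contents of the electronic record, and workers with no later visit could be missed.
- **The section 12 list is not exhaustive.** It is tempting to read it as barring vaccination data. Hemogram and serum biochemistry are scheduled in Tables 2 and 5 and are absent from it too, and 6.5 itself says that vaccinations are recorded. The omission is an inconsistency, not proof that the data go uncollected.
- **Most vaccinated workers never reach the spike analysis.** Never-positive workers are left out of the kinetics models, and the final cohorts in 6.5 rest on RT-PCR and nucleocapsid antibodies. A vaccine inducing only spike antibodies (an assumption) would not by itself move a worker into the infected cohort. This stands. One sentence in 6.6 describes the classifying ELISA as covering both N and S, however, and must be reconciled with the next paragraph, which names N only.
- **Vaccine protection.** A reader might conclude that it cannot be estimated. No listed outcome or planned analysis estimates it, and it would remain estimable if doses were recovered, so the point does not rest on it.
- **An entry question alone changes no planned result**, because no analysis uses vaccination. That is correct, and is why the entry record must be paired with separate reporting.

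**Conclusion.** The concern holds in a limited form. As written, the plan does not ensure that vaccination before the first sample is known, and it analyses all data from ever-positive workers without regard to vaccination. Spike IgG and spike-pool T-cell responses in those workers may therefore mix two sources, and severity comparisons may be confounded where vaccinated shares differ.

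The size cannot be fixed from the documents. It depends on when vaccination began, how entry was spread over the 441 days, how many entrants had been vaccinated, and the size of the vaccine effect. Under the assumptions shown, a vaccinated share of 10% to 20% is enough to shift a group mean by about the difference the study was sized to detect, while a share near zero makes the problem negligible for the current 1350. The 275 and 551 in the first table should not be read as numbers of vaccinated workers. Workers added under the planned enlargement to 2024 could also enter already vaccinated. The change is worth making because the information is cheap to obtain now and harder to obtain once participants have left.

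**What to change.** - In 6.5, record vaccination status, dates, product and number of doses at study entry as well as at each visit.
- Add vaccination to the variable lists in 6.6 and section 12, so that they agree with 6.5 and 6.7.
- Back-fill workers already enrolled, at the next visit or from the electronic record where it holds the information.
- In 6.8.2.1 and 6.8.2.2, report the spike IgG kinetics and the severity comparisons in workers unvaccinated at entry, with those vaccinated at entry shown separately. State the number with unknown status. Treat the spike-pool T-cell results in the same way.

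Doses given during follow-up also have no role in the planned analyses. They need their own rule, and the entry record is a precondition for it.

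The cost is one added question, a record check, a small amendment to the data lists, and a somewhat smaller sample for the main spike comparison.

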#### 6.5.1. RECRUITMENT

The Basic Prevention Unit of Northern Metropolitan Area of Barcelona (Primary Health Care and Hospital), Spain (NM\_BCN) offers HCW to participate in ProHEPIC-19 study, if they accept; the researchers of ProHEPiC-19 contact these participants.

Eligible participants interested in the study, are accurately informed about the ProHEPiC-19 protocol, and signed informed consent to participate.

Participants complete several clinical questionnaires and immune clinical determination at baseline, 7 days, 15 days, 3, 6, 9 and 12, 16, 20, 24 months after the beginning of the study. (see Table 2)

Participant data files will be stored in numerical order (code system) and in a secure and accessible place and manner. Participant files will be maintained in storage for a period of 15 years after completion of the study.

Anonymised demographic data will be collected for those participants who decline to take part in the project, to assess the external validity of the recruited sample of participants.

## 6.6 VARIABLES MAIN COVARIABLES

- 1) Biological sex measured as a dichotomous variable in two categories (Male, Female)
- 2) Age (years): registered and analyzed as a continuous variable
- 3) Academic level: measured as a 5 levels variable (lower primary, completed primary, secondary, Post-secondary non-tertiary education, Short-cycle tertiary education, university).
- 4) Housing characteristics (meters, number of bedrooms, number of people in the same house, relationship, age of them)
- 5) Work variables (professional category, schedule, workplace's characteristics)
- 6) Clinical Spectrum of COVID-19 defined on procedure for action against cases of infection with the new SARS-CoV-2 coronavirus, defined according to national and international guidelines ( asymptomatic, Mild-Moderate Illness, severe-critical ) as defined in section 6.5
- 7) Clinical monitoring of COVID-19 symptoms, days of duration and monitoring Long Covid symptoms. (Table 3 , Table 4)
- 8) The date of symptom onset shall be considered as the date of appearance of the first symptoms. These symptoms, which are described in Table 2, are the confirmation of a positive RT-PCR test or antigen test (IgM (N) or IgG (N)).
- 9) Diagnostics. In the electronic medical records (EMR) for Primary Care and Hospitals, the diseases are codified using the International Classification of Diseases, version 10 (ICD-10), including the specific codes for COVID-19
- 10) Use of personal protective equipment (working and in the free time)
- 11) Medication prescribed. Classification number of drugs according to the Anatomical Therapeutic Chemical (ATC) Classification System.
- 12) Hospital admissions: admissions and emergency procedures according to the codes ICD-10 used in CMBD-HA.
- 13) Comorbidities: diabetes, hypertension, ischaemic heart diseases, other chronic comorbidities
- 14) Mortality by all causes. The initial data for the calculation of risk of death will be determined from March 15, 2020.
- 15) Psychosocial and healthy habits changes during pandemic (dream, eating, sexuality, physical activity and familiar relationship)
- 16) Laboratory Assays

A) RT-PCR will be used as diagnostic test every 2 weeks RNA for RT-PCR tests will be extracted from fresh samples using the STARMag 2019-nCoV kit (Seegene, CA, USA) on a liquid-dispensing robot (STARlet Hamilton, USA). To inactivate the virus and extract viral RNA, 500 µl of the transfer medium containing the swab is combined with 500 µl of lysis buffer of the STARMag kit in a BSL-2 laboratory; following 10' of incubation at room temperature, 350 µl was used for nucleic acid extraction into a volume of 100 µl of extracted genome, from which 8 µl was taken for the 2019-nCoV PCR assay. The detection of RNA will be performed using the Allplex™ SARS-CoV-2 Assay is a multiplex real-time PCR

assay to detect 4 target genes of SARS-CoV-2 in a single tube. The assay is designed to detect RdRP, S and N genes specific for SARS-CoV-2, and E gene for all of Sarbecovirus including SARS-CoV-2 (Seegene, CA, USA) according to the manufacturer's instructions.

B) Quantification of antibodies to SARS-CoV-2. We performed a previous validations study with 6 different IVD-CE approved ELISA tests and selected the commercially available test kits - the AntiSARS-CoV-2 IgG and IgM ELISA (Inmunodiagnostic). This ELISA test had a Sensitivity 92.5% and a specificity 93.3% for IGM and IgG against Nucleocapsid (N) and Spike (S) antigens. For this, the best reagents and the most relevant antigen specificities will be analysed. We will perform test at baseline, 7 days, 15 days, 3, 6, 9 and 12,16,20,24 months after the beginning of the study.

We conducted a pre-validation study (March-April 2020) with 6 different IVD-CE approved ELISA tests and selected commercially available Anti-SARS-CoV-2 IgG and IgM ELISA kits (Inmunodiagnostic Limited ©). These ELISA tests had a sensitivity of 92.5% and a specificity of 93.3% for IGM and IgG against the nucleocapsid (N) antigen. Positivity thresholds were provided by the assay manufacturers and were considered positive with an index value greater than 1.1, indeterminate from 0.9 to 1.1 and negative if <0.9 index units.

Positive participants with Rt-PCR + or IgM (N) or IgG (N) were also tested for antibodies against the Spike (S) subunit of SARS-CoV-2. This was done by enzyme immunoassay for the qualitative determination of IgG class antibodies against COVID-19 (SARS-CoV-2) in human serum with DECOV1901. This reagent complies with the technical specifications for sensitivity, specificity, and standardisation according to WHO International Standards and Reference Panel for anti-SARS-CoV-2 antibody (WHO/BS.2020.2403). Positivity thresholds were provided by the assay manufacturers and were considered positive with an index value greater than 40, indeterminate from 32 to 40 and negative if <32 UI/ml

Positive participants for serology or/and RT-PCR were also tested for antibodies against the Spike (S) subunit of SARS-CoV-2. This was done by enzyme immunoassay for the quantitative determination of IgG class antibodies using DECOV1901 (Demeditec Diagnostics GmbH©). This reagent complies with the technical specifications for sensitivity, specificity, and standardisation according to WHO International Standards and Reference Panel for anti-SARS-CoV-2 antibody (WHO/BS.2020.2403). Positivity thresholds were provided by the assay manufacturers and were considered positive with an index value greater than 40, indeterminate from 32 to 40 and negative if <32 UI/ml

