**Secondary:**

1. To determine the kinetics of SARS-CoV-2 antibodies and cellular immune response in early, mid, and long periods of immunization.
2. To assess the relation between clinical variables and initial RT-PCR results with the interindividual differences in the immune response in early, mid, and long periods of immunization.
3. To analyze differentially expressed cytokines as biomarkers of disease progression in early, mid, and long periods of immunization.

**Methods and analysis:** Longitudinal, dynamic, prospective cohort study with a 12-month follow-up, which is being conducted in 4 primary-care centres and one hospital of Northern Metropolitana Nord of Barcelona (Spain). For now, the study consists of 1350 participants divided into 2 cohorts: 1) Healthy-Exposed HCWs: 675 not infected by SARS-CoV-2 (RT-PCR with a negative result and negative SARS-CoV-2 antibodies at baseline) and 2) Infected HCWs: 675 symptomatic participants (those with new persistent cough, temperature  $\geq 37.5^{\circ}\text{C}$ , anosmia, or ageusia or other compatible symptoms with COVID-19) or asymptomatic participants diagnosed by positive RT-PCR test and/or SARS-CoV-2 antibodies (IgM, IgG at baseline). Primary outcomes include: humoral and cellular immune response, quantitative antibodies to SARS-CoV-2, SARS-CoV-2 antibody levels related to progression phenotype, clinical spectrum of SARS-CoV-2, symptomatology, demographics and other variables that may be predictive of immune response.

**Follow-up:** baseline, 15 days, 1, 3, 6, 9 and 12 months.

**Findings to date:** Current literature has shown that the immune response is maintained for a minimum of 2 months. Nevertheless little is known about the association between the immune response and the progression phenotype of COVID-19.

**Future plans:** This prospective cohort offers the possibility to study associations between immune response and progression phenotype according to age and gender as well as long-term immune response. In turn, we will be able to examine possible cumulative effects, taking into account several

clinical variables. The study is ongoing and we plan to extend it to increase the size of the cohort until 2024.

**Ethics and dissemination:** The study is approved by the Ethics Committee (IDIAPJGol ref 20/067-PCV IGTP ref COV20/00660 (PI-20-205). Dissemination will occur through presentations at National and International conferences and publications in international peer-reviewed journals.

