### 6.8.1 STATISTIC TO MEET PRIMARY AIM: TO CONSOLIDATE A PROSPECTIVE COHORT OF HEALTH CARE WORKERS (HCW) TO GENERATE EPIDEMIOLOGICAL AND CLINICAL HIGH-QUALITY DATA.

A descriptive analysis of the participants will be performed using the number and percentage for categorical variables, and mean and standard deviation or median and quartiles 1 and 3 for quantitative variables. Frequency and percentage of followed-up patients and dropouts will be updated at each timepoint. Profiles of dropouts and visited people will be assessed using the appropriate statistical test in order to prevent potential biases due to drop out. Cohorts will be compared at each time point in terms of sociodemographic, epidemiological, clinical, and immunological information available. To analyze this, an exploratory bivariate analysis will be performed using the tests of Chi Square, ANOVA, Kruskall-Wallis, depending on the application conditions assumptions.

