**Table 4 Symptoms clinical monitoring\***

Symptom	Date of onset of the symptom	Duration (days)	Observations
Cardiovascular			
Fainting			
Pain/burning in chest			
Tachycardia			
Bradycardia			
Palpitations			
Visibly inflamed/ bulging veins			
Dermatologic			
COVID toe			
Dermatographia			
Other skin and allergy			
Peeling skin			
Petechiae			
Skin rashes			
Gastrointestinal			
Diarrhea			
Loss of appetite			
Vomiting			
Abdominal pain			
Nausea			
Constipation			
Gastroesophageal reflux			
Head/eyes/nose/ears/throat			
Runny nose			
Sore throat			
Hearing loss			
Other hearing/ear issues			
Tinnitus			
Vision symptoms			
Immunologic/autoimmune			
New allergies			
New anaphylaxis reaction			
Musculoskeletal			
Bone ache or burning			
Muscle aches			

Tightness of chest			
Joint pain			
Muscle spasms			
Neuropsychiatric			
Acute confusion/disorientation			
Changes to sense of smell and taste			
Dizziness, unsteadiness or balance issues			
Hallucinations			
Headaches and related symptoms			
Insomnia			
Other sleeping symptoms			
Sleep apnea			
Slurring eord/speech			
All neurological sensations			
Brain fog			
Memory issues			
Neuralgia (nerve pain)			
Speech/language issues			
Tremors			
Vibrating sensations			
Pulmonary/Respiratory			
Dry cough			
Rattling of breath			
Breathing difficulty (normal O2 saturation level)			
Cough with mucus production			
Coughing blood			
Other respiratory and sinus			
Shortness of breath			
Sneezing			
Reproductive/genitourinary/ endocrine			
All menstrual issues			
Bladder control issues			

Systemic			
Elevated temperature (98.8-100.4F)			
Fever ( $>100.4F$ )			
Chills/flushing/sweats			
Fatigue			
Low temperature			
Other temperature issues			
Post exertional malaise			

*\*Characterizing Long COVID in an International Cohort: 7 Months of Symptoms and Their Impact* *Hannah E. Davis1\*, Gina S. Assaf1\*, Lisa McCorkell1\*, Hannah Wei1\*, Ryan J. Low1,2\*, Yochai Re'em1,3\*, Signe Redfield1, Jared P. Austin4, Athena Akrami1,2\*+ medRxiv preprint doi:*  
<https://doi.org/10.1101/2020.12.24.20248802>

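### Symptom duration, including Long COVID, is recorded in days with no end date or ongoing marker and no censoring rule, so unresolved symptoms are understated by an amount that depends on observation time.

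*Combined protocol and SAP*

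**What the plan says.** Section 6.6 lists "Clinical monitoring of COVID-19 symptoms, days of duration and monitoring Long Covid symptoms" as covariable 7 and points to Tables 3 and 4. Table 4 has one row per symptom. Besides the symptom name its columns are "Date of onset of the symptom", a duration counted in days, and observations. It has no end date, no resolved/ongoing column and no date of last assessment.

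Section 6.5 says that symptoms are collected again after entry: "At subsequent visits, epidemiological data, clinical data (symptoms) and vaccinations are recorded". It gives no rule for entering a symptom that is still present, or for carrying it forward from one visit to the next.

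Section 6.8 names no analysis of symptom duration. The general rule in 6.8.1 is "mean and standard deviation or median and quartiles 1 and 3 for quantitative variables". For comparing the cohorts at each time point, 6.8.1 adds that "an exploratory bivariate analysis will be performed using the tests of Chi Square, ANOVA, Kruskall-Wallis, depending on the application conditions assumptions". No censoring rule or time-to-event method appears anywhere in 6.8.

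The documents give the length of follow-up in two ways. The abstract describes a "Longitudinal, dynamic, prospective cohort study with a 12-month follow-up". Section 6.5.1 schedules questionnaires at "baseline, 7 days, 15 days, 3, 6, 9 and 12, 16, 20, 24 months after the beginning of the study".

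**The concern.** A duration is known only once the symptom has ended. For a symptom still running at last contact, the days counted so far are a lower bound. On the Table 4 layout, 90 days for a symptom that resolved and 90 days for one still present look the same. A mean, a median, an ANOVA or a Kruskal-Wallis test would then treat both as completed durations.

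This matters most for Long COVID, where the symptoms of interest are those most likely to be unresolved. Recorded durations would be too short, and more so for workers observed for less time. If observation time differs between the groups compared, part of any difference in duration would reflect that. Ongoing status that is not recorded at the visit may also be impossible to recover later, above all for workers who drop out.

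**Working it through.** **The plan's own figures.** The documents give no figure for symptom duration. Their one design figure reproduces: an exact noncentral F calculation with η² = 0.01, alpha 0.05 and 90% power gives 522 per group (power 0.9005), and 522/0.9 = 580 after dropout. Nothing below depends on it.

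**Inputs from the documents**
- Follow-up: 12 months (abstract), taken as 365 days, or 24 months (6.5.1), taken as 730 days.
- Recruitment (6.3): 31 March 2020 to about 15 June 2021, which is 365 + 76 = 441 days.
- Observed time already differs between workers: 6.8.2.1 reports antibody values beyond 450 days for only 14 participants.

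**Assumptions (not in the documents)**
- Long symptoms last an exponential time with true median M of 90, 180 or 365 days, so the mean is m = M/ln 2 = 130, 260 or 527 days.
- Acute symptoms are exponential with median 14 days.
- Long symptoms make up 10%, 30% or 100% of all symptoms.
- Observed time is either fixed at L days or uniform on 0 to 441 days. The second case would arise from an analysis at the close of recruitment.

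**Formulas**
- Unresolved at L: 2^(−L/M).
- Mean recorded when cut at L: m(1 − 2^(−L/M)).
- Unresolved when observed time is uniform on 0 to A, with A = 441: (m/A)(1 − e^(−A/m)).
- Median recorded under uniform observed time: the x that solves 2^(−x/M)(1 − x/A) = 0.5.

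**Long symptoms only**

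| True median | Unresolved at 365 d | Recorded mean at 365 d (true) | Unresolved at 730 d | Unresolved, uniform 0–441 d | Recorded median, uniform 0–441 d |
|---|---|---|---|---|---|
| 90 d | 6% | 122 (130) | under 1% | 28% | 68 d |
| 180 d | 25% | 196 (260) | 6% | 48% | 108 d |
| 365 d | 50% | 263 (527) | 25% | 68% | 149 d |

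Worked line for M = 180: 2^(−365/180) = 0.245, and 260 × (1 − 0.245) = 196. With A/m = 441/259.7 = 1.698, (1 − e^(−1.698))/1.698 = 0.48.

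A simulation with 400,000 draws per scenario agrees with these shares to within one percentage point. In the uniform case the correlation of recorded duration with observed time is 0.37, 0.54 and 0.71 for the three medians. Kaplan-Meier with an ongoing marker returns medians of 90, 180 and 367 days, against recorded medians of 68, 108 and 149.

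**Acute and long symptoms together (10% or 30% long)**
- Unresolved: 1% to 15% at 12 months, and 7% to 24% with uniform observed time.
- Overall median: largest shift from 24 to 22 days.
- Mean: can fall far. With 30% long and M = 365, the true mean is 0.7 × 20.2 + 0.3 × 526.6 = 172 days, and the recorded mean under uniform observed time is about 65.
- Correlation with observed time: 0.11 to 0.28.

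The 365- and 730-day columns show why the two follow-up statements must be reconciled: for M = 365 the unresolved share is 50% under one and 25% under the other.

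**The case against.** The strongest reply is that duration is part of one covariable out of 16, is not a listed outcome, and has no analysis of its own. The one symptom analysis named in 6.8.2.2 is a chi-squared comparison of prevalence. That is right. That durations would be summarised as complete is an inference from the general rule in 6.8.1, not a stated intention. But no other rule is offered for a quantitative clinical variable.

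Second, staggered entry does not by itself make follow-up unequal. Workers may each be followed for the full schedule, no common data cut-off is stated, and comparisons at each time point largely equalise time since entry. This also stands, so the uniform 0–441 day case is an illustration. It does not remove the problem: even with complete 12-month follow-up, some long symptoms are unresolved. Time since onset can still vary, because Table 2 gives workers with non-recent infection no visit until visit 4. The sample size section also allows for 10% dropout.

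Third, ongoing status might be pieced together from onset date, duration, observations and later symptom reports, and the actual case report form is not reproduced. That is possible, but no rule provides for it.

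A reader might go further and infer that Long COVID durations will mainly measure length of follow-up, or that groups with identical true duration will differ two- to threefold. The second inference has correct arithmetic: with mean durations of 180 and 365 days, m(1 − e^(−L/m)) gives 71 against 156 days and 80 against 231 days for L = 90 and 365, ratios of 2.2 and 2.9. But it assumes that every symptom is long and that one whole group is observed for 90 days and the other for 365. The documents contain no such contrast. Follow-up dominates only when symptoms are very long relative to observed time.

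**Conclusion.** The point holds as a gap in data capture and in the analysis rule. Table 4 cannot separate a finished symptom from an ongoing one, and no method in 6.8 allows for censoring. Durations of symptoms unresolved at last contact will be understated and will depend partly on observation time.

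The size cannot be fixed from the documents, because neither the unresolved share nor the distribution of durations is given. Under the assumed exponential durations it runs from minor (6% of long symptoms unresolved, true median 90 days, full 12 months) to dominant (68% unresolved, true median 365 days, uniform observed time). For all symptoms pooled with 10% to 30% long, the median is nearly unaffected and the mean is the vulnerable summary. The sample size and the listed primary and secondary outcomes are untouched. This is a worthwhile, inexpensive improvement and does not threaten the study's main aims.

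**What to change.** 1. Add to Table 4 an end date and a yes/no field for whether the symptom is still present at the visit, with the date last assessed.
2. State in 6.8 that symptom duration is analysed as time from onset to resolution, with ongoing symptoms censored at the last assessment. Use Kaplan-Meier curves and log-rank tests where end dates are available. Where status is known only at visits, use an interval-censored method. This replaces means and ANOVA or Kruskal-Wallis for this variable.
3. Reconcile the 12-month follow-up in the abstract with the 24-month schedule in 6.5.1, since follow-up length sets the censoring time.

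The cost is a few form fields and standard survival code. The main burden is retrospective: entries already made without an end date must be checked against later visits, and some may remain unclear.
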